9.3.3 Interim Analysis

There will be no interim analysis for futility or early efficacy due to the small sample size in the AGC cohort and fast enrollment in the HCC cohort with hypothesized median PFS of 10 months under the alternative hypothesis.

9.4 Stopping Rules

Let P_T be the true probability that a patient experiences a treatment-related SAE (as defined in Section 5.2.1) within the first cycle of treatment in the AGC cohort. The trial will stop if there is statistical evidence that P_T exceeds 30%. We will use a Bayesian sequential design by checking whether P_T exceeds this threshold value after 6, 15, and 21 patients are evaluable for SAEs. The decision rule is to stop the trial if the posterior probability that P_T exceeds 0.30 is 0.97 or more; $P(P_T > 0.3 | data) > 0.97$. A noninformative prior distribution for P_T will be used.

Table 1 gives the stopping rules for the design at each look and column 2 gives the maximum number of patients with treatment-related SAEs in order for the trial to proceed. For example, if 4 or more treatment-related SAEs are observed after enrolling 6 patients, the trial stops. The third column gives the probability of stopping the trial when in fact, the true $P_T = 0.30$. This is the equivalent of the Bayesian type I error probability. The target type I error probability was set at 0.10.

Number of Patients	Number to Continue	Probability to Stop	Cumulative Probability to Stop
6	3	0.070	0.070
15	7	0.028	0.098
21	10	0.006	0.104

Table 1. Stopping rules based on three interim looks. Number to continue is the maximum number of treatment-related SAEs for not stopping the trial.

Table 2 gives the design operating characteristics under selected values of the true probability P_{T} . It gives the probability of stopping the trial under the alternative hypothesis, the expected sample size, and the average sample size given that the trial stopped. For example, if the true value of P_{T} is 0.5, then there is an 63.6% chance that the trial is stopped early, and the average sample size is about 14.5. On the other hand, there is a small chance of stopping the trial if P_{T} is small; 1.9% chance of stopping the trial when in fact $P_{T} = 0.2$.

	True Value	Probability to	Expected	Expected
	of P ⊤	Stop	N	N given that we Stopped

IIT2020-11-[name]-TELAT

0.20	0.0197	20.73	7.3	
0.30	0.1043	19.78	9.2	
0.40	0.3212	17.66	10.6	
0.50	0.6362	14.50	10.8	

Table 2. Design operating characteristics under different scenarios for the true probability of toxicity P_{T} .

Similar stopping rules are used for the HCC cohort with a target probability of treatment-related SAEs not to ne exceeded equal to 0.3. Tables 3 and 4 present the operating characteristics of this stopping rules for HCC arm.

Number of Patients	Number to Continue	Probability to Stop	Cumulative Probability to Stop
6	3	0.070	0.070
15	7	0.028	0.098
24	11	0.010	0.108

Table 3. Stopping rules based on three interim looks. Number to continue is the maximum number of treatment-related SAEs for not stopping the trial.

True Value	Probability to	Expected	Expected
of P ⊤	Stop	N	N given that we Stopped
0.20	0.0198	23.67	7.46
0.30	0.1087	22.48	10.03
0.40	0.3480	19.79	11.90
0.50	0.6866	15.79	12.05

Table 4. Design operating characteristics under different scenarios for the true probability of toxicity P_{T} .

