4.0 PATIENT ELIGIBILITY

Enrollment will follow the safety stopping rules described in Section 9.4, with interim looks after completion of the first cycle of treatment for the 6th subject in each cohort, and again after completion of the first cycle of treatment for the 15th subject in each cohort. Any enrollment holds deemed necessary for the evaluation of stopping rules will be at the discretion of the PI.

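### Section 9.4 gives its safety stopping limit in two units, patients and SAEs, and the printed stopping probabilities hold only when patients are counted

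*Combined protocol and SAP*

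**What the plan says.** Statements in Section 9.4 that count patients:

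- The parameter: "Let P_T be the true probability that a patient experiences a treatment-related SAE" within the first cycle, in the AGC cohort.
- The decision rule, which is a statement about that parameter: "The decision rule is to stop the trial if the posterior probability that P_T exceeds 0.30 is 0.97 or more".
- The sentence introducing column 2 of Table 1: "the maximum number of patients with treatment-related SAEs in order for the trial to proceed".

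Statements in Section 9.4 that count events:

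- The worked example, which comes next: "if 4 or more treatment-related SAEs are observed after enrolling 6 patients, the trial stops".
- The note to Table 1, repeated word for word under Table 3 for HCC: "Number to continue is the maximum number of treatment-related SAEs for not stopping the trial".

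The limits to continue are 3, 7 and 10 at 6, 15 and 21 patients (AGC), and 3, 7 and 11 at 6, 15 and 24 patients (HCC). Section 5.2.1 defines which SAEs count (non-hematologic, grade 3 or 4, probably related or related to telatinib, first cycle). It is also written in events and does not say how to treat two in one patient.

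On timing, the example places the first look at enrollment of six patients. The opening paragraph of Section 9.4 places the AGC looks "after 6, 15, and 21 patients are evaluable for SAEs", and Section 4.0 calls for "interim looks after completion of the first cycle of treatment for the 6th subject in each cohort", and again after the 15th.

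**The concern.** A patient can have more than one qualifying SAE in the first cycle, and the two units then part. Suppose two of the first six patients each have two. Counted in patients, the tally is 2, within the limit of 3. Counted in SAEs, it is 4, and the worked example stops the trial. The same data give opposite decisions under two sentences of one section.

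The rule can halt a cohort after six patients, so one patient counted twice can decide the outcome. For HCC, the note under Table 3 is the only statement of the unit placed beside the limits. Whenever some patients have more than one counted SAE, counting events makes the rule stop an acceptable regimen more often than the tables say.

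**Working it through.** **Inputs.** Limits, look sizes, the 0.30 threshold, the 0.97 posterior cut-off and the 0.10 target come from Section 9.4. The prior is described there only as noninformative; I take Beta(1,1), an assumption supported by step 2.

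**1. Reproduce the printed probabilities, counting patients.** Each patient is an independent yes/no outcome with probability P_T. At P_T = 0.30 the first look gives

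P(4 or more of 6) = 0.0595 + 0.0102 + 0.0007 = 0.0705.

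Carrying forward only the paths that continue gives 0.0278 at 15 and 0.0060 at 21 (AGC), total 0.1043. For HCC the third look gives 0.0104, total 0.1087. Both match the plan. At P_T = 0.20, 0.40 and 0.50 the totals are 0.0197, 0.3212 and 0.6362 (AGC) and 0.0198, 0.3480 and 0.6866 (HCC), also as printed. Expected N matches in every row.

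**2. Reproduce the limits.** With x affected patients of n, the posterior is Beta(1+x, 1+n−x), and P(P_T > 0.30 | data) = P(Bin(n+1, 0.30) ≤ x).

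| Look | Posterior at the limit (continue) | Posterior at one more (stop) |
|---|---|---|
| 6 | 3/6: 0.874 | 4/6: 0.971 |
| 15 | 7/15: 0.926 | 8/15: 0.974 |
| 21 (AGC) | 10/21: 0.961 | 11/21: 0.986 |
| 24 (HCC) | 11/24: 0.956 | 12/24: 0.983 |

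Every limit is the largest patient count whose posterior is below 0.97. The limits and the printed probabilities are therefore both per patient.

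**3. Test the conflict on one data set.** Two of six patients affected, two SAEs each:

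- Posterior rule: P(Bin(7, 0.30) ≤ 2) = 0.0824 + 0.2471 + 0.3177 = 0.647, below 0.97, so continue.
- Worked example: 4 SAEs, so stop.

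**4. Size if SAEs were counted.** Keep P_T = 0.30 and let a share q of affected patients have a second counted SAE. Each patient then contributes 0, 1 or 2 with probabilities 1−P_T, P_T(1−q) and P_T·q. The first look becomes

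P(4 or more patients) + P(3 patients)·[1−(1−q)³] + P(2 patients)·q².

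At q = 0.10: 0.0705 + 0.1852 × 0.271 + 0.3241 × 0.01 = 0.0705 + 0.0502 + 0.0032 = 0.1239. The later AGC looks add 0.0572 and 0.0162, total 0.197. The same recursion over all looks gives:

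| q (assumed) | AGC, P_T = 0.30 | HCC, P_T = 0.30 | AGC, P_T = 0.20 |
|---|---|---|---|
| 0 (as printed) | 10.4% | 10.9% | 2.0% |
| 2% | 12.3% | 12.8% | 2.6% |
| 5% | 15.1% | 15.8% | 3.6% |
| 10% | 19.7% | 20.7% | 5.3% |
| 20% | 28.8% | 30.4% | 9.0% |
| 30% | 37.4% | 39.6% | 13.1% |

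At P_T = 0.30 the false-stop rate doubles at q of about 11% and triples at about 22-23%.

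**5. Timing.** P_T covers the whole first cycle, so a patient only just enrolled has not yet had the chance to show the outcome. The example's wording does not fit that definition; the other two timing statements do.

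**The case against.** The strongest reply is that Section 9.4 already has a patient-based rule. P_T is per patient, the sentence labelled as the decision rule concerns P_T, and the sentence just before the example says patients. The example only illustrates that sentence, and two SAEs in one patient cannot be two successes in a per-patient probability. A careful statistician would count patients. This stands, and it limits the point to conflicting wording.

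Three stronger readings are tempting, but the documents do not support them.

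- A reader might infer that the plan sets its limit in SAEs, so that a patient with two counts twice. That follows only if the example and notes override the definition, and nothing says they do. Nor does any section say that those applying the rule would use the table notes in preference to the decision rule.
- A reader might infer that the false-stop rate will double or triple. That needs about 11% or 22-23% of affected patients to have a second counted SAE. The documents give no such rate, and Section 5.2.1 makes the counted event narrow. At 2% or 5% the AGC rise is to 12.3% or 15.1%.
- A reader might infer that looks will be taken at enrollment and so pass an unacceptable regimen. One loose phrase would have to override both the evaluability wording in Section 9.4 and Section 4.0, which ties the first two looks to completion of cycle 1.

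The reply does not remove the inconsistency: the example and both notes state the limit in the wrong unit, and no sentence says that a patient counts once.

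**Conclusion.** The point holds as an internal inconsistency in a decision threshold. The definition, the posterior rule and the introduction to column 2 count patients; the example and the notes to Tables 1 and 3 count SAEs. The printed error rates (10.4% AGC and 10.9% HCC at P_T = 0.30, against a target of 10%) belong to the patient count only.

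The harm is conditional. It arises only if the example or notes are applied as written, and its size depends on the unknown share q: for AGC, 12.3% to 37.4% as q runs from 2% to 30%. These figures also assume independent patients and at most two counted SAEs each. The error runs toward stopping too often. The timing mismatch is minor, because two other statements already settle when patients are assessed. The design, limits and tables are sound. The wording should be settled before a look is taken.

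**What to change.** - In the worked example and in the notes to Tables 1 and 3, replace the count of treatment-related SAEs with a count of *patients with at least one treatment-related SAE (Section 5.2.1) in cycle 1*.
- In the worked example, reconcile the enrollment-based timing with the evaluability wording in the same section and with Section 4.0.

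The cost is a few wording edits. No limit, table value or data collection changes. Waiting for cycle 1 adds no new delay to the first two looks, since Section 4.0 already requires it.

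No new denominator rule is needed. Requiring every counted patient to have completed cycle 1 or had a qualifying SAE would be a new evaluability rule. It could conflict with Section 5.7 (one telatinib dose makes a patient evaluable for toxicity) and Section 5.8 (only withdrawals before telatinib starts are replaced), and could leave fewer than 21 or 24 patients at the last look.

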ECG	Electrocardiogram
ECOG	Eastern Cooperative Oncology Group
HCC	Hepatocellular carcinoma
HRPP	Human Research Protections Program
INR	International normalized ratio
IV (or iv)	Intravenously
MTD	Maximum Tolerated Dose
ORR	Overall Response Rate
OS	Overall Survival
PBMCs	Peripheral Blood Mononuclear Cells
PD	Progressive Disease
PFS	Progression Free Survival
PO	per os/by mouth/orally
PR	Partial Response
PT	Prothrombin time
SAE	Serious Adverse Event
SD	Stable Disease
ULN	Upper limit of normal
WBC	White Blood Cells
WOCBP	Women of childbearing potential

STUDY SCHEMA

Title	A Phase II Study Evaluating Safety and Efficacy of Telatinib in Combination with Keytruda in Subjects with Advanced Stomach and Gastroesophageal Junction Cancers or Hepatocellular Carcinoma	
Protocol Number	IIT2020-11-[name]-TELAT	
Phase	Phase II	
Methodology	Single arm, open label study with two parallel cohorts	
Study Duration	Approximately 30 months (anticipated accrual duration 12 months, with up to an estimated 12 months on-treatment and up to an estimated 6 months follow-up) Stopping rules for safety will be followed.	
Study Center	Cedars-Sinai Medical Center and affiliates	
	Primary:	
	The primary objective is to assess progression-free survival (PFS) in subjects with advanced gastric cancer or HCC receiving telatinib 900 mg BID in combination with Keytruda.	
	Secondary:	
	The secondary objectives are to assess:	
Objectives	Overall response rate (ORR), Disease Control Rate (DCR), Overall survival (OS), and Safety	
	Exploratory:	
	Time to Progression (TTP)	
	Change in inflammatory cytokines	
	Change in plasma metabolites	
	Change in immune cell profile	
	Change in stool microbiome	
	21 subjects with advanced gastric cancer	
Number of Subjects	24 subjects with advanced hepatocellular carcinoma	
Diagnosis and Main Inclusion Criteria	Adult subjects with advanced gastric cancer or HCC who are indicated for Keytruda	
Study Product(s), Dose,	Telatinib 900 mg (3 x 300 mg tablets) will be administered orally, twice daily.	
	Keytruda will be administered IV 200 mg every 3 weeks.	
Duration of administration	Until disease progression, intolerable toxicities, or withdrawal of consent	
Statistical Methodology Gastric cancer: PFS will be compared to KEYNOTE-059 with a endpoint of improvement in PFS from 2.0 months to 4 months. HCC: PFS will be compared to KEYNOTE-224 with a primary e of improvement in PFS from 4.9 months to 10 months		

STUDY SUMMARY

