9.0 STATISTICAL CONSIDERATIONS

9.1 Sample Size

For the AGC cohort, the median PFS in the KEYNOTE-059 trial (Fuchs et al. 2020) is 2.0 months. Assuming an accrual time of 12 months and 6 months follow-up, 21 patients are needed to improve median PFS from 2 months to 4 months or HR = 0.5 with 80% power using a two-sided one sample log-rank test at the 0.05 level of significance. Time to progression was assumed to follow an exponential distribution.

For the HCC cohort, the median PFS in the KEYNOTE-224 trial (Zhu et al. 2018) is 4.9 months. Assuming an accrual time of 12 months and 10 months follow-up, 24 patients are needed to improve median PFS from 4.9 months to 10 months or HR = 0.49 with 80% power using a two-sided one sample log-rank test at the 0.05 level of significance. Time to progression was assumed to follow an exponential distribution.

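### Does Section 9.4 overstate the chance that the gastric cohort is stopped early for toxicity when the true SAE rate is 50%?

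*Combined protocol and SAP*

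**What the plan says.** The Study Schema plans "21 subjects with advanced gastric cancer", and Section 9.1 gives the same number: "21 patients are needed to improve median PFS from 2 months to 4 months". Section 9.4 checks whether the SAE probability "exceeds this threshold value after 6, 15, and 21 patients are evaluable for SAEs". Table 1 lets the cohort continue with at most 3, 7 and 10 affected patients at the three looks; the text spells out the first: "if 4 or more treatment-related SAEs are observed after enrolling 6 patients, the trial stops". Table 2 then lists, for four true rates, a probability to stop, an expected N, and an expected N given a stop. The sentence in question reads the last row of that table into prose: "then there is an 63.6% chance that the trial is stopped early, and the average sample size is about 14.5".

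Two other places bear on what counts as early. The table captions treat every look alike: "Table 1. Stopping rules based on three interim looks", and for the liver cancer (HCC) cohort "Table 3. Stopping rules based on three interim looks". Section 4.0, on enrolment, names a look after the 6th subject, "and again after completion of the first cycle of treatment for the 15th subject in each cohort", and no third one.

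**The concern.** The look at 21 takes place when all planned AGC patients have been enrolled and have completed their first cycle. A reader who sees the word *early* next to an average sample size will naturally take it to mean before the cohort is full. On that reading the 63.6% is too high, because it includes crossings at 21. An IRB or monitoring committee using the sentence to judge how well the rule limits exposure to a toxic combination would infer a 36.4% chance (1 − 0.636) that all 21 patients are enrolled at a 50% SAE rate, when the figure is 43.2% (1 − 0.568). The two looks named in Section 4.0, set against three in the captions, seem to confirm that the status of the last look was not settled.

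**Working it through.** **Inputs.** Looks at 6, 15 and 21 patients; stop at 4 or more, 8 or more, and 11 or more affected patients (one above each limit in Table 1); true rate 0.5 (Table 2, last row). The calculation uses the printed limits, so it does not depend on which noninformative prior was chosen. As a side check, a uniform prior (my assumption; Section 9.4 does not name one) gives posterior probabilities of 0.9712 at 4/6, 0.9743 at 8/15 and 0.9860 at 11/21, all at or above 0.97. One fewer event at the later looks gives 0.9256 (7/15) and 0.9613 (10/21). The limits in Table 1 therefore follow from the stated rule.

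**Look at 6.** P(X ≥ 4) for X ~ Bin(6, 0.5) = (15 + 6 + 1)/64 = 0.3438.

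**Look at 15.** Sum over s = 0 to 3 of P(s events in 6) × P(at least 8 − s events in the next 9):
(1×10 + 6×46 + 15×130 + 20×256)/(64×512) = 7356/32768 = 0.2245.

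**Look at 21.** Only paths that passed both earlier looks with 5, 6 or 7 events can reach 11. Their path counts at 15 patients are 2862, 4410 and 4950, and they need at least 6, 5 or 4 events in the last 6 patients:
(2862×1 + 4410×7 + 4950×22)/(32768×64) = 142632/2097152 = 0.0680.

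**Plan's own figures.**
- Any look: 0.3438 + 0.2245 + 0.0680 = 0.6362 after rounding (unrounded 0.63625). Table 2 prints 0.6362.
- Expected N: 6×0.34375 + 15×0.22449 + 21×0.43176 = 14.50. Table 2 prints 14.50.
- Expected N given a stop at any look: (6×0.34375 + 15×0.22449 + 21×0.06801)/0.63625 = 10.78. Table 2 prints 10.8.

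**Before full enrolment.** 0.34375 + 0.22449 = 0.5682, so the last look supplies 6.8 points. Restricted to the first two looks, the expected N given a stop would be (6×0.34375 + 15×0.22449)/0.56824 = 9.56. Table 2's 10.8 therefore shows that the plan counts a crossing at 21 as a stop.

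**Other true rates**, from the same recursion (HCC limits 3, 7 and 11 at 6, 15 and 24):

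| True rate | Looks at 6 or 15 (both cohorts) | Any look, AGC | Any look, HCC |
|---|---|---|---|
| 0.2 | 1.9% | 2.0% | 2.0% |
| 0.3 | 9.8% | 10.4% | 10.9% |
| 0.4 | 28.9% | 32.1% | 34.8% |
| 0.5 | 56.8% | 63.6% | 68.7% |

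The any-look columns agree with Tables 2 and 4. At the design value of 0.3 the last AGC look adds 0.6 points, which Table 1 already prints as 0.006.

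**The case for a change.** The best case for a correction is that the sentence joins *early* to a sample size. In the average of 14.5, a crossing at 21 contributes 21 patients, exactly as completing the cohort does, so in terms of patients spared only the 56.8% counts. This is also the only worked example of the rule's behaviour at a high SAE rate, and rewording it would cost almost nothing. The 56.8% is itself a best case: Section 4.0 leaves enrolment holds to the PI's discretion, and patients enrolled while a look matures would lower it.

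The numbers stand, and so does the ambiguity of the word. Three parts of the argument do not carry further.

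- The average of 14.5 cannot show which probability the sentence meant. A crossing at 21 and a completed cohort both count as 21, so the average is the same under either reading.
- *Early* has a sound second meaning. Section 9.4 speaks of stopping the trial and does not limit that to accrual. The look at 21 comes once the last patient has finished a three-week cycle, while Section 5.5 foresees up to an estimated 12 months on treatment and then survival follow-up. Some patients would be off treatment by then, but a stop would still cut the trial short for the rest.
- Section 4.0 need not conflict with the captions. It governs enrolment and lists the two looks that can affect enrolment; the look at 21 or 24 cannot.

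**Conclusion.** The concern does not call for a change. The 63.6% is the correct probability of crossing at one of the three looks, and the tables in Section 9.4 are right as labelled. What remains is one loosely chosen word in an illustrative sentence for one cohort; the HCC text does not use it. Read strictly as before full enrolment, the figure would be 56.8%, a difference of 6.8 points at a true rate of 0.5 and 0.6 points at 0.3, assuming no enrolment beyond a look while its data are awaited. A reader who wants that figure has what is needed in Section 9.4: the looks, the limits and, through Section 9.1, the cohort size.

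Nothing operational rests on the wording. The limits 3/7/10 and 3/7/11, the 0.97 threshold, the type I error figures and the expected sample sizes of 14.50 and 15.79 at a true rate of 0.5 are the same either way, and the committee's action at each look is fixed by the limits. Adding columns for stopping before full enrolment would bring in a figure that depends on there being no overrun, which the plan does not guarantee. Renaming the 21/24 look a final assessment could suggest that it no longer stops the trial, contrary to Section 9.4.

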10.0 STUDY MANAGEMENT

10.1 Conflict of Interest

Any reportable conflict of interest will be disclosed to the local IRB and will be outlined in the Informed Consent Form.

10.2 Institutional Review Board (IRB) Approval and Consent

It is expected that the IRB will have the proper representation and function in accordance with federally mandated regulations. The IRB should approve the consent form and protocol.

In obtaining and documenting informed consent, the investigator should comply with the applicable regulatory requirement(s) and should adhere to Good Clinical Practice (GCP) and to ethical principles that have their origin in the Declaration of Helsinki.

Before recruitment and enrollment onto this study, the patient will be given a full explanation of the study and will be given the opportunity to review the consent form. Each consent form must include all the relevant elements currently required by the FDA Regulations and local or state regulations. Once this essential information has been provided to the patient and the investigator is assured that the patient understands the implications of participating in the study, the patient will be asked to give consent to participate in the study by signing an IRB-approved consent form.

Prior to a patient's participation in the trial, the written informed consent form should be signed and personally dated by the patient and by the person who conducted the informed consent discussion.

